Similar to the exercise stress test, participants in the intervention arm may experience uncomfortable physical sensations due to exercising, including sore muscles, fatigue, and shortness of breath. If the participant has new cardiac-related symptoms since his/her last cardiology check-up that are concerning to the participant, the interventionist (i.e. PA coaches)

will recommend contacting the participant's cardiologist and the study procedures are put on hold until the cardiologist clears the participant to return to the study. The interventionist also contacts the study PI, [name], who notifies the participant's cardiologist that the participant is experiencing symptoms.

During videoconferencing, PA coaches conduct sessions in privacy and encourage participants to do the same. The same will be encouraged for those who participate in the focus groups. Coaches undergo the same training as other research staff at NCH, including completing Collaborative Institutional Training Initiative (CITI) certification and a day-long instructional seminar on protecting human subjects. Videoconferencing has a lower risk of privacy breach than email communications. Should technical difficulties (e.g., WiFi issues, recorder error) occur during the videoconferencing sessions, PA coaches will make adjustments in accordance with privacy and confidentiality guidelines to conduct the session and/or document the content of the session. These adjustments may include (but are not limited to) conducting the session as a voice call (in the event of videoconferencing issues) or writing a summary of the session (in the event of recorder error). Audio recordings and other documents resulting from these adjustments will be stored on the hospital's secure OneDrive platform. For the purposes of identifying and problem-solving common technical difficulties, PA coaches will record all videoconferencing, recording, and other technical and practical issues. This record will also help identify sessions that may not be available for fidelity evaluation.

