4 STUDY DESIGN

This single-site study is a randomized clinical trial of a Fitbit and exercise prescription vs. a Fitbit, exercise prescription, AND videoconferencing sessions with a PA coach over the course of 8 sessions in 20 weeks.

For Phase 1, participants are asked to complete less than 30-45 minutes of questionnaires wear an accelerometer for 7 days, and undergo an exercise stress test. Once the exercise stress test is completed and the accelerometer is returned, participants are compensated \$100. Parking and mileage reimbursement to/from the hospital is provided.

If a participant engages in <150 minutes of MVPA per week and has no contraindications on the exercise stress test, he/she is approached for participation in Phase 2. Once recruited, participants receive a Fitbit and an explanation of their exercise prescription based on the results of their exercise stress test as provided by an exercise physiologist. If the exercise physiologist is not available to develop the exercise prescription, the principal investigator, in consultation with the study physician, will develop the exercise prescription based on guidelines provided by the exercise physiologist. Next, study staff open an envelope (pre-prepared by the study statistician, [name]) to reveal the participant's study arm designation. Randomization is stratified by the number of minutes spent in MVPA per the accelerometer data in Phase 1 (≤ 25 min/day of MVPA vs. $\geq 26-59$ min/day of MVPA) with randomly varying block sizes.

Participants are randomized to 1 of 2 arms: the comparison arm, which receives a Fitbit and the exercise prescription, or the intervention arm, which also receives a Fitbit and exercise prescription PLUS videoconferencing sessions (e.g., FaceTime, Google Hangouts or Skype) with a PA coach (8 sessions over the course of 20 weeks). Each session lasts approximately 30 minutes and is audiotaped. The intervention arm focuses on changing attitudes (e.g., identifying pleasurable physical activities), perceptions of social norms of PA (e.g., problem-solving ways to receive support from family and friends) and perceptions of control for engaging in PA (e.g., increasing self-efficacy through goal setting and reducing barriers), as outlined by the Theory of Planned Behavior, to increase time spent in MVPA and decrease SB. The Fitbit is used to facilitate goal setting and self-monitoring for participants in the intervention arm.

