5.7 Assessment of Subject Compliance with Study Intervention

Participant compliance in the intervention arm is monitored in two ways. First, participants are asked to wear a Fitbit, which is used by the coaches to assess the participants' engagement in MVPA. Coaches request that participants in the intervention arm sync their Fitbit each day so that coaches may monitor their PA levels and incorporate feedback during sessions. Participants' attendance at each session is documented. For those participants in the comparison arm, they are told to sync their Fitbit regularly upon first receiving the Fitbit, but are not contacted about the Fitbit again.

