6.3 Phase 2: Enrollment in the RCT

Eligible participants from Phase 1 are met at their home (or the hospital if preferred) to receive their Fitbit and exercise prescription, which is based on the results of their stress test. Home visits may also be conducted virtually (e.g., via Google Hangouts). Participants completing virtual home visits will receive study materials by postal mail or email as appropriate. After receiving the Fitbit and exercise prescription, the participant's arm designation is revealed by opening an envelope that has been prepared by the study statistician, [name]. Prior to opening the envelope, the study PI, study staff, and the participant are blind to the study arm designation.

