6.4 Interim Assessment (between weeks 8-12)

Participants in both arms are asked to complete an interim assessment (between weeks 8-12), which includes:

Interim online questionnaire: Participants are asked to complete the same questionnaire that was completed at Baseline, with the exception of those in the comparison arm receiving questions about changes to their health since Baseline.

Benefits of PA⁵¹

Subjective Norms survey⁵²

Social Support for Exercise survey⁵³

Barriers to Exercise survey⁵⁴

Self-Efficacy for Exercise Scale⁵⁵

Patient-Reported Outcomes Measurement Information System⁴⁶⁻⁴⁸

International Physical Activity Questionnaire^{49,50}

Cardiac Anxiety Questionnaire⁵⁶

Changes in Health

Physical Activity Stages of Change Questionnaire – Algorithm⁵⁸

Physical Activity Stages of Change Questionnaire - Continuous⁵⁹⁻⁶¹

MVPA and SB: Participants wear an accelerometer again for the same period (7 days) as the Baseline assessment and complete self-monitoring PA logs in the case they cannot wear the accelerometer (e.g. swimming).

Compensation: Participants are compensated \$50 for completion of the interim assessment survey and wearing the accelerometer for at least 4 days (1 weekend day, 3 weekdays), for at least 10 hours per day.

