6.5 Post-Intervention (between weeks 20-26)

Participants in both arms are asked to complete a post-intervention assessment (between weeks 20-26), which includes:

Post-intervention online questionnaire: Similar items are included on the post-intervention questionnaire as with the baseline and interim assessment with the exception that participants are asked to rate the intervention on multiple dimensions.

Benefits of PA⁵¹

Subjective Norms survey⁵² Social Support for Exercise survey⁵³

Barriers to Exercise survey⁵⁴

Self-Efficacy for Exercise Scale⁵⁵

Patient-Reported Outcomes Measurement Information System⁴⁶⁻⁴⁸

International Physical Activity Questionnaire^{49,50}

Cardiac Anxiety Questionnaire⁵⁶

Changes in Health

Post-Intervention Satisfaction

Physical Activity Stages of Change Questionnaire – Algorithm⁵⁸

Physical Activity Stages of Change Questionnaire - Continuous⁵⁹⁻⁶¹

MVPA and SB: Participants wear an accelerometer again for the same measurement period (7 days) as in previous assessments and complete self-monitoring PA logs in the case they cannot wear the accelerometer (e.g. swimming).

VO_{2max}: VO₂ measurement is obtained again with a graded exercise stress test using a modified Bruce protocol. Participants who were found to have an arrhythmia or show evidence of cardiac ischemia during exercise stress testing will be immediately referred to their cardiologist for follow-up.

Compensation: Participants are compensated \$100 for completion of the post-intervention survey, exercise stress test, and returning the accelerometer with at least 4 days (1 weekend day, 3 weekdays), for at least 10 hours per day of data. Additionally, participants parking and mileage to/from the hospital for the exercise stress test are reimbursed.

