The current study has several procedures in place to reduce the likelihood of serious medical adverse events. Potential participants' cardiologists are notified prior to being recruited for the study and excluded if the cardiologist has communicated or documented any concerns about that young adult engaging in MVPA. All participants undergo a baseline exercise stress test and are not approached for recruitment for Phase 2 if contraindications are detected in Phase 1. In the rare event that a participant has an acute medical event during the exercise stress test, appropriate hospital procedures are enacted, which include calling an emergency response team and immediate evaluation by a cardiologist. The same procedures used for patients undergoing exercise stress testing as part of a medical evaluation are initiated and followed. During the course of the intervention, if a young adult reports cardiac symptoms that are concerning to the participant and are new since the last cardiac evaluation, PA coaches are trained to request that the young adult contact their cardiologist. Young adults have given the study PI, [name], permission to talk with the cardiologist in the instance that a concerning and/or new cardiac symptom is reported. All study procedures are put on hold until the young adult is evaluated by the cardiologist and cleared to proceed with the study.

If a participant was to report bothersome emotional symptoms to study staff during the course of the study, [name], a licensed psychologist, will contact the participant to evaluate the severity of their emotional symptoms. If the participant is not in danger of harming themselves or someone else, [name] will assist the participant in identifying mental health resources. If the participant is positive for significant suicidal or homicidal ideation (i.e., positive for intent, has a plan, and has the means by which to execute a plan), [name] will notify the participant that confidentiality must be broken and the local authorities will be contacted.

7.1.2 Procedures to be Followed in the Event of Abnormal Test Values or Abnormal Clinical Findings

Incidental findings from the exercise stress test are communicated to the participant and the participant's cardiologist. The cardiologist will make a determination as to whether the participant may proceed with the study if an abnormal event, or incidental finding, is detected.

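### Both arms exercise on a study-issued prescription, but the step for a new cardiac symptom is written only as something a coach starts

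*Combined protocol and SAP*

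**What the plan says.** **Both arms are prescribed exercise.** Section 4 describes "the comparison arm, which receives a Fitbit and the exercise prescription". Section 6.3 has eligible participants met at home or at the hospital "to receive their Fitbit and exercise prescription, which is based on the results of their stress test", before the arm is revealed. Under Section 6.2 the prescription covers how often, how long, how hard and what type of activity.

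**The symptom step.** Section 7.1.1 (Safety Procedures) deals with a young adult who, during the intervention, reports a cardiac symptom that is concerning and new since the last cardiac evaluation. In that case, "PA coaches are trained to request that the young adult contact their cardiologist". It then says: "All study procedures are put on hold until the young adult is evaluated by the cardiologist and cleared to proceed with the study". Section 2.3.1 gives the same step and names the interventionist, identified as the PA coach, as the person who starts it. That paragraph opens by saying that "participants in the intervention arm may experience uncomfortable physical sensations due to exercising".

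**Comparison-arm contact.** Section 5.7 says these participants are told to sync the Fitbit when they first receive it "but are not contacted about the Fitbit again". The interim questionnaire in Section 6.4 repeats the baseline one, except for "those in the comparison arm receiving questions about changes to their health since Baseline". The post-intervention questionnaire in Section 6.5 lists "Changes in Health". Section 7.1.1 adds that at both questionnaires the comparison arm is asked about medical attention sought.

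**The concern.** The participants in both arms have moderate or complex CHD and are asked to exercise on a plan the study gave them. Cardiologist approval and the baseline stress test screen them beforehand, but neither can detect a symptom that starts later. During the exercise period the protocol's answer to such a symptom is to send the participant to cardiology and hold study procedures until clearance.

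That answer is reached only through a coach. A comparison participant with the same symptom has, on the text available, no instruction on what to do and no staff member trained to give one. Unless they act unprompted, the study may first hear of it at the next questionnaire. One of the procedures that should wait for clearance is the post-intervention stress test, which comparison participants also undergo.

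**Working it through.** The plan states no figure on this point, so the check is a comparison of text plus subtraction on the schedule.

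**1. Who can trigger the step.** It appears in Sections 2.3.1 and 7.1.1. In both, a PA coach starts it, and only the intervention arm has coaches (Sections 4 and 5.4). The hold sentence in 7.1.1 is not limited to one arm; its stated trigger is. The next paragraph of 7.1.1, on emotional symptoms, is framed around any participant reporting to study staff, so the cardiac step is narrower than its neighbour.

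**2. Whether another stated contact fills the gap.** The text messages in Section 5.4 are sent between sessions, so they belong to the coached programme, and their content is described as motivational or encouraging. Section 7.1.1 says events may come to light at other study contacts, but its only example is intervention meetings. No scheduled comparison-arm contact is stated between the Phase 2 visit and the interim assessment, or between the two assessments.

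**3. Whether the arm-neutral rules fill it.**
- Section 7.3: the cardiology team decides on suspension for cardiac-related adverse events and unanticipated problems. The study must first know of the event.
- Adverse event definition (7.1.1): a cardiovascular symptom change counts only if it led the participant to seek medical attention. A new symptom not yet taken to a doctor does not meet it. Deterioration of a condition present at screening is also recorded as an adverse event, but it too must first be known.
- Section 5.5: the prescription may change if the cardiologist recommends it.
- Section 5.3.2: participation may end if the cardiologist so determines or the participant asks.

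Each of these acts after someone has spoken up. The coach's prompt is what produces that first contact.

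**4. Length of the intervals.** Inputs: interim window weeks 8 to 12 (6.4), post-intervention window weeks 20 to 26 (6.5). Week 0 is taken as the Phase 2 visit (assumption).
- Visit to first health question: 8 to 12 weeks.
- First to second, shortest: 20 − 12 = 8 weeks.
- First to second, longest: 26 − 8 = 18 weeks.
- If the post-intervention assessment is at week 22, as Section 7.3 states: 22 − 12 = 10 to 22 − 8 = 14 weeks.

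**5. Number affected.** 40 / 2 = 20 with equal allocation (implied, not stated), or about 17 on the per-arm figure in Section 5.

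**The case against.** The strongest reply has three parts.

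**Routes to a hold exist.** Sections 7.3, 5.5 and 5.3.2 apply to both arms, and the attending cardiologist knows of the study and can see the stress-test results. A reader might infer that a comparison participant cannot be held or suspended at all. The documents do not support that: a participant who calls the cardiologist reaches someone able to modify or stop participation. What is unstated is only the prompt to call.

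**The instruction may sit elsewhere.** The consent form, the Manual of Procedures and the Data and Safety Monitoring Plan are not in the documents reviewed, and any of them could tell participants whom to contact. This stands, and limits the point to what the protocol text states.

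**The contrast between arms is modest.** Sessions include no scheduled symptom check, so intervention participants must also volunteer symptoms, and their longest gap between sessions is 20 − 12 = 8 weeks. Coaches also encourage that arm to do more, which is a reason for coach-specific safeguards. The comparison arm has its own health-change questions, whose wording is not shown and which may capture symptoms without care sought. All this lowers the stakes. It does not supply a prompt between assessments.

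Three further inferences should be resisted:
- A reader might add the 8 weeks allowed between stress test and Phase 2 visit to the first interval. The prescription is handed over only at that visit, so those weeks contain no study-prescribed exercise.
- A reader might take the hold as a rule to stop exercising. The protocol holds study procedures; it states no stop-exercise rule for either arm.
- Section 7.5 counts symptom-driven cardiologist contacts for the treatment arm, and a reader might infer that the DSMB is not told of comparison-arm events. Sections 7.2.1 and 7.5 report adverse events without arm restriction, and the Protocol Summary calls both arms treatment arms.

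**Conclusion.** The point holds in a limited form. The symptom-triggered step is written only as a coach's action, so the comparison arm has no stated symptom-triggered prompt during intervals of 8 to 12 weeks and then 8 to 18 weeks. It concerns 20 participants, or about 17, depending on which of the plan's figures is used.

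This rests on two assumptions: that week numbers run from the Phase 2 visit, and that no document outside those reviewed already gives comparison participants the instruction. The documents give no symptom rate, so no count of missed or delayed symptoms is claimed. The change is worth making because it improves participant safety at almost no cost. It does not alter the feasibility aims or their analysis.

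**What to change.** 1. In Sections 2.3.1 and 7.1.1, state the existing step for all Phase 2 participants, whoever learns of the symptom.
2. With the exercise prescription, give each participant a written instruction: if a new, concerning cardiac symptom occurs, contact your cardiologist and notify study staff, with the staff role to contact named.
3. State that the existing hold-until-cleared rule applies to both arms and includes the post-intervention stress test.
4. Leave any advice on pausing exercise to the cardiology team.
5. Extend the exercise-discomfort sentence in Section 2.3.1 to both arms.
6. If the consent form already gives the instruction, cross-refer to it and align the wording.

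Cost: a short handout at a visit that already takes place, and edits to two sections. The downside is a few extra cardiology and study contacts in an arm meant to have minimal contact.

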7.1.3 Other Medical Events

Medical events not meeting the above definition of an adverse event.

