7 ASSESSMENT OF SAFETY

7.1 Methods and Timing for Assessing, Recording, and Analyzing Safety Parameters

7.1.1 Adverse Events

Definition

For the current study, an adverse event is an unanticipated change in cardiovascular, musculoskeletal, or emotional symptoms that are (1) concerning to the participant and (2) results in seeking medical attention, if cardiovascular or musculoskeletal in nature. Any condition that is present at the time that the participant is screened will be considered as baseline and not reported as an adverse event. However, if the study participant's condition deteriorates at any time during the study, it will be recorded as an adverse event. Serious adverse events are defined as adverse events that are severe in classification (as described below). We do not anticipate any serious adverse events due to study procedures. Adverse events that occur for participants during the course of the study are comprehensively documented, including events during the stress test, symptoms reported during the course of the intervention from participants in the intervention arm, dates and reasons for pauses in the study protocol due to symptom reporting, and determination of ability to proceed by participants' cardiologists. All unscheduled cardiology outpatient visits, visits to urgent care or the emergency department, unscheduled hospitalizations, or any other changes in health are documented. Participants in the comparison arm are asked whether they sought medical attention in the aforementioned contexts during the interim and post-intervention questionnaires. Additionally, the occurrence of any adverse event or serious adverse event may come to the attention of study staff during other study contacts (e.g., intervention meetings).

Classification

All adverse events and serious adverse events will be assessed by the PI and the study physician, [name], according to the guidelines outlined here.

Severity: The following guidelines will be used to describe severity:

- Mild: Events require minimal or no treatment and do not interfere with the participant's daily activities.
- Moderate: Events result in a low level of inconvenience or concern with the therapeutic measures. Moderate events may cause some interference with functioning.
- Severe: Events that require in-patient hospitalization and/or resulted in death or permanent disability.

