7.2 Reporting Procedures

7.2.1 Adverse Events

Any adverse events are reported to the DSMB at each meeting and to the NCH IRB annually.

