7.4 Halting Rules

If it is found that the study intervention is related to an unexpected serious adverse event, an ad hoc meeting will commence that will include the PI, study physician, and the DSMB to determine if enrollment needs to be temporarily suspended until a safety review is convened. If a safety review is conducted, the DSMB will decide whether the study should continue per protocol, proceed with

caution, be further investigated, be discontinued, or be modified and then proceed. Suspension of enrollment (for a particular group or for the entire study) is another potential outcome of a safety review.

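### A new hospitalization, permanent disability or death outside three symptom groups is not a serious adverse event and has no stated reporting rule unless it qualifies as an unanticipated problem

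*Combined protocol and SAP*

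**What the plan says.** Section 7.1.1 of the combined protocol and SAP states that "an adverse event is an unanticipated change in cardiovascular, musculoskeletal, or emotional symptoms that are (1) concerning to the participant", with the second condition that the change "results in seeking medical attention, if cardiovascular or musculoskeletal in nature". A condition present at screening counts as baseline, but if the participant's "condition deteriorates at any time during the study, it will be recorded as an adverse event".

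Seriousness is built on that definition: "Serious adverse events are defined as adverse events that are severe in classification". The Severe category covers in-patient hospitalization, death and permanent disability. The same section also has unplanned admissions and any other health changes documented, whatever the body system.

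Section 7.1.3 sets up the residual class in one sentence: "Medical events not meeting the above definition of an adverse event". Section 7.1.4 defines unanticipated problems with no body-system limit. They must be unexpected, at least possibly related to the research, and suggestive of greater risk than was known.

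On reporting, section 7.2.1 says "Any adverse events are reported to the DSMB at each meeting and to the NCH IRB annually". Section 7.2.2 covers serious adverse events and section 7.2.3 covers unanticipated problems. The DSMB summaries in section 7.5 list adverse events and serious adverse events, but not the 7.1.3 class. The meeting in section 7.4 is called "If it is found that the study intervention is related to an unexpected serious adverse event".

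**The concern.** Because a serious adverse event must first be an adverse event, the limit to three symptom groups carries over to the serious class. A participant could be admitted, permanently disabled or die from something outside those groups, and under the protocol's own wording the event would not be serious.

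Two things are at stake. First, if the event is judged unrelated, no rule puts it before the DSMB, IRB or NHLBI, so none of them is placed to question that judgement or to see how such events fall by arm. Second, if it is judged at least possibly related, it moves on a different clock from other events of the same severity and cannot by itself call the section 7.4 meeting.

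**Working it through.** No figure in the plan needs reproducing. The check traces one event through the definitions in 7.1.1, 7.1.3 and 7.1.4, the reporting rules in 7.2.1 to 7.2.3, the DSMB report content in 7.5 and the trigger in 7.4. The event requires admission, or causes permanent disability or death, and lies outside the three symptom groups.

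| Case | Class | DSMB | IRB | NHLBI | 7.4 meeting |
|---|---|---|---|---|---|
| A. Worsening of a condition present at screening | Serious adverse event, if the deterioration clause carries no body-system limit | 5 business days if related and unexpected, otherwise each meeting | 5 business days if related and unexpected, otherwise annually | If unexpected: 7 calendar days when fatal or life-threatening, otherwise 15 | Yes, if related and unexpected |
| B. New, and not an unanticipated problem | 7.1.3 only | None stated | None stated | None stated | No |
| C. New, and an unanticipated problem | Unanticipated problem that is not a serious adverse event | 2 weeks | Not named in 7.2.3 | 14 days | No |

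**Case B against the serious route.** Were the event in case B a serious adverse event, section 7.2.2 would send it to the DSMB at a meeting and to the IRB annually even if unrelated. If unexpected, it would also go to NHLBI within 7 or 15 calendar days, and that rule has no relatedness test. As a 7.1.3 event it has none of these. Case B is chiefly the event judged unrelated. It also takes in an event that was expected, or that does not suggest greater risk.

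**Case C against the serious route.** Take 5 business days as 7 calendar days (an assumption: no public holiday).

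- DSMB: 14 − 7 = 7 calendar days later.
- NHLBI, fatal or life-threatening: 14 − 7 = 7 days later.
- NHLBI, other: 15 − 14 = 1 day earlier, so about the same.
- IRB: 5 business days under 7.2.2 for a related, unexpected event; no time given in 7.2.3.

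**Moving from B to C.** Section 7.1.1 has the PI and study physician assess adverse events and serious adverse events, and its relatedness and expectedness categories are worded for adverse events. No such assessment is stated for 7.1.3 events. The step that would recognise one of them as an unanticipated problem is therefore unspecified.

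**The case against.** A reader might infer that an event outside the three groups can never be serious and need never reach an oversight body. The documents do not support that.

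- The deterioration clause repeats no body-system limit. Worsening of known epilepsy or asthma that leads to admission can be an adverse event, hence serious (case A).
- The unanticipated-problem class covers any body system and reaches both the DSMB and NHLBI. The events of most safety interest, those that are unexpected, possibly related and suggestive of greater risk, do have a route.
- Section 7.4 is not the only safeguard. Sections 5.3.4 and 10.5 leave the DSMB a general power to end the study, and 5.3.4 gives the IRB one too.
- It would also be wrong to read 7.1.3 as purely a body-system class. It equally holds cardiovascular, musculoskeletal or emotional events that fail another condition, such as care not having been sought where required.
- Heat illness or breathlessness on exercise might be called cardiovascular in this population, so such cases do not illustrate the gap cleanly.
- The trial is small and classed as minimal risk. No event rate is given from which to argue that an imbalance between arms would be visible, and the feasibility outcomes are untouched.
- The Data and Safety Monitoring Plan cited in 7.5 and the institutional policy cited in 7.2.2 are not in these documents and may contain a rule.

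All of this narrows the point. It does not give case B a reporting rule, and the general stopping power helps little with events that no rule puts before the DSMB.

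**Conclusion.** The gap is real and limited. A new in-patient hospitalization, permanent disability or death outside cardiovascular, musculoskeletal or emotional symptoms is documented but has no stated reporting rule, unless it qualifies as an unanticipated problem. If it does qualify, the DSMB notice comes about a week later than for a related, unexpected serious adverse event. The NHLBI notice is a week later only for fatal or life-threatening events, the IRB is not named, and section 7.4 is not triggered. It concerns both arms, up to 40 randomized participants. The number of such events cannot be estimated from the documents.

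The conclusion rests on three assumptions. The deterioration clause is taken to mean conditions present at screening, as the sentence before it suggests. If it meant the participant's health in general, little would be left in 7.1.3, but the three-group limit would then have little purpose. The terms are taken at their written meaning. And the finding is about this protocol text only, not about the plan and policy that it cites.

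This should be corrected because following the written rule leaves serious outcomes outside oversight. It does not affect the trial's analysis.

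**What to change.** Keep the present adverse event definition for non-serious events. In section 7.1.1, define a serious adverse event as any medical event, of any body system, that meets the existing Severe criteria: in-patient hospitalization, death or permanent disability. Word the relatedness and expectedness categories so that they cover these events. The assessment by the PI and study physician, the section 7.2.2 clocks and section 7.4 then apply without further change. In section 7.5, add the remaining 7.1.3 events, tabulated by arm, to the DSMB report.

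Simply deleting the three symptom groups from the adverse event definition is not advised. The care-seeking condition applies only to cardiovascular and musculoskeletal events, so every other unanticipated symptom that worried a participant, a cold included, would become a reportable adverse event with no threshold.

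The cost is a few sentences and one extra row in the DSMB table. The events are already documented, so no new data collection is needed. The downside is a few more, mostly unrelated, events to assess and forward.
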